# 8.12. Nasal Discharge Collection from Paper Tissues

Each participant will be given pre-weighed packets of paper tissues. Participants will be asked to place single tissues used for nose blowing or sneezing into a specified bag (for that participant only).

A daily 24-hour collection will take place throughout the quarantine period. Distribution of paper tissues and bags will start on Day -1, with the first collection on Day 0. Thereafter distribution and collection of tissues will occur at the same time points (±1 hour) with tissues distributed 24 hours ahead. Tissues will be handed out daily and collection will occur until the discharge from quarantine.

In the event of a participant staying in quarantine beyond the planned day of discharge, the 24-hour distribution and collection of tissues and bags will continue until the participant is finally discharged from quarantine.

24-hour paper tissue collections will be analysed to determine the following over the quarantine period:

- 24-hour nasal discharge weight.
- The number of paper tissue used for nasal discharge over 24-hour period.

# 8.13. Electrocardiogram

Study specific normal ranges are provided in Appendix 4.

Twelve-lead ECGs will be obtained to evaluate the electrical activity of the heart. ECGs will be read on site by an appropriately qualified Investigator. Wherever possible the same Investigator will review subsequent ECGs from the same participant for the assessment of any change from baseline.

Any changes from baseline during the study will be assessed for their clinical significance. Clinically significant changes will be reported as AEs. The PI or delegate will assess non-clinically significant changes to determine whether they should be recorded.

## 8.14. Spirometry

Spirometry will be performed according to hVIVO's procedures. Height at screening will be used as the baseline measurement for all spirometry assessments.

Spirometry should meet the American Thoracic Society/European Respiratory Society guidelines criteria (Miller et al. 2005). For FEV1 and forced vital capacity (FVC), the highest value from a minimum of

three technically satisfactory attempts will be considered. For FEV1 and FVC the highest and the second highest value should not exceed more than 150 mL or 5% (whichever is greater). If the difference is larger, up to eight technically acceptable measurements will be made with repeatability assessed after each additional attempt. If after eight technically acceptable attempts the difference remains greater than 150 mL or 5% (whichever is greater) the highest values will be reported, and an operator comment will be made to the source data. FEV1 and FVC will be assessed and reported as the highest values regardless of curve.

Predicted values will be calculated according to the formula of the European Coal and Steel Community.

Spirometry may be repeated at any time in the event of respiratory signs or symptoms (repeated coughing, bradypnea, tachypnoea, rales, and rhonchi) or respiratory difficulties.

## 8.15. Questionnaires

#### Patient Health Questionnaire (PHQ-9) and Generalised Anxiety Disorder Questionnaire (GAD-7)

PHQ-9 and GAD-7 questionnaires will be used to assess participants' eligibility and current mental state regarding ability to tolerate isolation in the Quarantine Unit.

## 8.16. Blood Samples

A maximum volume of 550 mL of blood may be taken from each participant for any given 8-week period. If additional samples are required in excess of this amount, e.g., to monitor abnormalities, these will be collected at the discretion of the Investigator.

#### 8.16.1. Safety Blood Analysis and Assessments

Appendix 2 describes the safety blood tests that will be performed including, but not limited to, serology, haematology, coagulation, biochemistry, thyroid function test and cardiac enzymes. Additional safety assessments will be conducted at the discretion of the PI/Investigator, as required.

Serum samples will be tested for serum FSH in post-menopausal female participants only and for serum pregnancy test in all female participants.

#### 8.16.2. Challenge Virus Serology Samples

A participant must be serosuitable to take part in the study, i.e., he/she must have no or low pre-existing serum levels of antibodies specific to the Challenge virus. This antibody titre cut-off for serosuitability will be described in the AP.

Serum levels of pre-existing Virus specific antibodies to the Challenge virus will be determined using HAI influenza or as described in the AP.

#### 8.16.3. Pharmacokinetic Blood Samples

Blood samples for determination of SAB-176 serum concentrations will be collected as outlined in the pharmacokinetic (PK) sampling schedule below:

#### Sampling schedule:

Day 1 (IMP / placebo administration day): one sample pre-infusion and one sample at 1-hour post-infusion end (infusion end includes any time required for flushing), and at Days 2, 4, 6, 8, and 28.

The allowable time windows for the sampling are as follows:

- $\pm 5$  minutes from the scheduled time for time points  $\leq 1$ -hour post-infusion end.
- Allowable time windows from the scheduled time for time points >1-hour post-infusion end:
  - Day 2 timepoint (24 hours after infusion end): ±1 hour window.
  - $\circ$  Day 4 timepoint (72 hours after infusion end): ±2 hours window.
  - $\circ$  Day 6 timepoint (120 hours after infusion end): ±2 hours window.
  - $\circ$  Day 8 timepoint (168 hours after infusion end): ±2 hours window.
  - Day 28 timepoint (648 hours after infusion end): ±2 days window.
- There is no time window requirement for the pre-infusion sample. The pre-infusion PK sample must be taken on the same day prior to infusion.

Blood samples will be transported, processed, and stored in accordance with the AP. Pharmacokinetic analysis will be performed using HAI and neutralisation assays against the H1N1 strain at each participant collection timepoint. This analysis will be conducted at both hVIVO and Sponsor designated laboratories.

#### 8.16.4. Anti-drug Antibodies

Blood (serum) samples will be collected to measure the incidence of ADAs to SAB-176 during the trial and follow the same sampling schedule for the PK blood samples as outlined in Section 8.16.3.

Blood samples will be transported, processed, and stored in accordance with the AP. ADA sample evaluations will be performed by the Sponsor designated laboratory.

#### 8.16.5. Blood for Immunology Biomarker Evaluations

Blood may be used for exploratory analysis related to viral infection, for example:

- Genomics (e.g., GWAS, SNPs).
- Transcriptomics (e.g., microarray, RNA sequencing).
- Immunological markers (proteomics, cytokines, and chemokines)

## 8.17. Nasal Samples

Nasal sampling procedures will be performed for the following purposes during the study:

- Respiratory Pathogen Screen.
- Influenza discharge test.
- Viral load assays.
- Exploratory purposes:
  - Nasal PK
  - Viral resistance
  - Immunological markers.

Where any nasal sampling time points occur together the order of sampling will typically be (1) nasosorption or mid turbinate swab, (2) nasopharyngeal swab (3) nasal wash.

Tolerance of the nasal procedure(s) may be determined at the screening visit, as appropriate.

Remaining cells and epithelial lining fluid from the nasopharyngeal swabs may be stored for exploratory purposes.

#### 8.17.1. Respiratory Pathogen Screen

On entry to quarantine, a nasopharyngeal swab (or nasal wash) will be collected and tested to detect the presence of a set of respiratory pathogens that could potentially contraindicate a participant's participation in the study. The methodology to be used to conduct the respiratory virus screen will be documented in the AP. Additional test may be conducted if the results from the first test were invalid to support study eligibility prior to virus inoculation, or if a community acquired infection is suspected during quarantine.

Any additional screening tests will be conducted at the discretion of the PI.

#### 8.17.2. Rapid Influenza Discharge Test

A rapid viral antigen test will be used to determine the presence of influenza only in a nasopharyngeal swab (or nasal wash) sample taken prior to discharge from the Quarantine Unit on Day 8. A qualitative PCR screening test may be used as an alternative test for this purpose.

#### 8.17.3. Viral Load

Nasopharyngeal swabs (or nasal washes) will be collected for viral load assays. Viral load may be determined by qRT-PCR and a cell-based infectivity assay (TCID50) if PCR positive, to investigate the following parameters:

- infectivity status and rate.
- viral dynamics (e.g., duration, peak, time to peak).

#### 8.17.4. Exploratory Analyses

#### 8.17.4.1. Nasal Pharmacokinetics

Nasal sample aliquots (nasosorption / mid turbinate swab) may be processed, stored, and analysed for exploratory PK analysis in accordance with the AP.

#### 8.17.4.2. Viral Resistance

A portion of each nasal sample may be processed, stored, and analysed for resistance analysis, in accordance with the AP.

#### 8.17.4.3. Immunology

A portion of each nasal sample may be processed, stored, and analysed for immunological markers, in accordance with the AP.

# 8.18. Recording of Adverse Events and Serious Adverse Events

The PI/Investigator is responsible for ensuring that all AEs, SAEs, and pregnancies are identified, evaluated, recorded, and reported in a timely manner as per Regulatory requirements and hVIVO's SOPs, and also for ensuring that the medical management (including follow up) of AEs, SAEs and, where appropriate, pregnancy symptoms/complications is provided by competent Investigator site staff.

The Sponsor of the study will also perform an evaluation of seriousness, causality, and expectedness of all SAEs.

The definitions of an AE or SAE, as well as the method of recording, evaluating, and assessing causality of AE and SAE and the procedures for completing and transmitting AE, SAE, and other reportable safety event reports can be found in Appendix 3.

#### 8.18.1. Time Period and Frequency for Collecting AE and SAE Information

All AEs / SAEs will be collected from the signing of the study specific ICF until the last follow-up visit at the time points specified in the SoA (Section 1.2).

Investigators are not obligated to actively seek AE or SAE after conclusion of the study participation. However, if the Investigator learns of any SAE, including a death, at any time after a participant has been discharged from the study, and he/she considers the event to be reasonably related to the study intervention or study participation, the Investigator must promptly notify the Sponsor.

#### 8.18.2. Method of Detecting AEs and SAEs

The method of recording, evaluating, and assessing causality of AE and SAE and the procedures for completing and transmitting SAE reports are provided in Appendix 3.

Care will be taken not to introduce bias when detecting AEs and/or SAEs. Open-ended and non-leading verbal questioning of the participant is the preferred method to inquire about AE occurrences.

#### 8.18.3. Follow-up of AEs and SAEs

After the initial AE / SAE report, the Investigator is required to proactively follow each participant at subsequent visits/contacts. All AEs / SAEs will be followed until resolution, stabilisation, the event is otherwise explained, or the participant is lost to follow-up (as defined in Section 7.3). Further information on follow-up procedures is provided in Appendix 3.

#### 8.18.4. Regulatory Reporting Requirements for SAEs

Prompt notification by the Investigator to the Sponsor of a SAE is essential so that legal obligations and ethical responsibilities towards the safety of participants and the safety of a study intervention under clinical investigation are met.

The Sponsor has a legal responsibility to notify both the local regulatory authority and other regulatory agencies about the safety of a study intervention under clinical investigation. The Sponsor will comply with country-specific regulatory requirements relating to safety reporting to the regulatory authority, Research Ethics Committee (REC) and Investigators.

Investigator safety reports must be prepared for SUSARs according to local regulatory requirements and Sponsor policy and forwarded to Investigators, as necessary.

An Investigator who receives an investigator safety report describing an SAE or other specific safety information (e.g., summary or listing of SAEs) from the Sponsor will review and then file it along with the Investigator's Brochure and will notify the REC, if appropriate according to local requirements.

Further information on regulatory reporting requirements is provided in Appendix 3.

## 8.18.5. Pregnancy

Details of all pregnancies in female participants and, if indicated, female partners of male participants will be collected from signing study specific ICF onwards until the last study assessment as outlined in the SoA (Section 1.2). If a pregnancy is reported, the Investigator should inform the Sponsor within 24 hours of learning of the pregnancy and should follow the procedures outlined in Appendix 3.

Abnormal pregnancy outcomes (e.g., spontaneous abortion, foetal death, stillbirth, congenital anomalies, ectopic pregnancy) are considered SAEs.

## 8.19. Treatment of Overdose

For this study, any dose of any drug administered as part of the study greater than the dose prescribed by the protocol will be considered an overdose.

In the event of an overdose. the Investigator should:

- 1. Contact the Medical Monitor immediately.
- 2. Closely monitor the participant for any AE/SAE and laboratory abnormalities associated with overdose and participants will be clinically followed up until the AE has resolved.
- 3. Document the quantity of the excess dose as well as the duration of the overdose in the CRF.

The Sponsor is responsible for notifying the Medicines and Healthcare Regulatory Agency (MHRA) and REC of the potential serious breach within 7 days of becoming aware of it.

## 8.20. Pharmacokinetics

Further details on PK sampling and analysis are outlined in Section 8.16.3 and 8.17.4.1.

Drug concentration information that may unblind the study will not be reported to blinded study site personnel until the study has been unblinded.

## 8.21. Pharmacodynamics

Pharmacodynamic parameters are not evaluated in this study.

# 8.22. Genetics

A blood sample for DNA isolation will be collected from participants who have consented to participate in the genetic analysis component of the study. Participation is optional. Participants who do not wish to participate in the genetic research may still participate in the study.

Details on processes for collection and shipment and destruction of these samples can be found in the AP.

# 9. Statistical Considerations

## 9.1. Statistical Hypotheses

The main study hypothesis is that treatment with SAB-176 will reduce the VL-AUC as determined by qRT-PCR in healthy adult participants after they have been challenged with Influenza A/California/2009 H1N1 virus when compared to treatment with placebo. The conclusions on efficacy will be based on the result of the primary analysis. Some other statistical tests will be performed for illustrative and exploratory purposes only. Consequently, no adjustment for multiplicity will be performed.

# 9.2. Sample Size Determination

Up to 60 participants will be inoculated with the Challenge virus.

The statistical powering selected for this study is estimated to be sufficient for the primary objective and based upon only the primary endpoint. The targeted power for this study's endpoint is for 80% using a two-sided type-one error rate of 5%. The sample size of 60 participants (30 in each arm) will allow detecting a 60% relative reduction in the qRT-PCR-AUC virology with SAB-176 assuming an 81% coefficient of variation in the control arm (taking into consideration Watson et al. 2015, Sloan et al. 2020).

The PCR-AUC data is based on log transformed PCR data.

The sample size indicates the number of participants to be inoculated with the Challenge virus.

# 9.3. Populations for Analyses

Population	Description
Enrolled	All participants who signed the study specific ICF, their eligibility is confirmed, and have been inoculated with the Challenge virus.
Randomised	All enrolled participants randomly assigned to study intervention.
Intent to Treat (ITT) Analysis Set	All participants randomly assigned to study intervention who received the study intervention (SAB-176 or placebo).
The Intent to Treat Infected (ITT-I)	All participants randomly assigned to study intervention who received the study intervention and were infected with Challenge virus as per the definition of laboratory confirmed infection for this protocol
Per Protocol (PP) Analysis Set (or Evaluable set)	All participants randomly assigned to study intervention who received the study intervention (ITT Analysis Set participants) who have no major protocol deviation likely to impact the efficacy evaluation, and who complete the quarantine period up to the final day of quarantine, (Day 8).

The following populations are defined:

Population	Description
Safety Analysis Set	All participants randomly assigned to study intervention and who received at least one dose of study intervention. Participants will be analysed according to the intervention they actually received.
PK Analysis Set	All participants randomly assigned to study intervention with at least three post-dose PK results.

The primary efficacy analysis will be on the PP Analysis Set. The ITT and ITT-I Analysis Sets will be used for supportive analyses on all or part of the primary and secondary efficacy endpoints, as defined in the Statistical Analysis Plan (SAP). The safety evaluation will be performed on the Safety Analysis Set. Additional analysis sets may be defined in the SAP.

## 9.4. Statistical Analyses

This section is a summary of the planned statistical analyses of the most important endpoints including primary and key secondary endpoints.

Venn Life Sciences will perform the statistical analyses for the study.

Data will be analysed and reported using SAS® version 9.4 or later.

#### 9.4.1. Statistical Analysis Plan

The SAP will be developed by Venn Life Sciences and approved by the Sponsor. The SAP will be finalised and signed prior to any look at unblinded of the data. The SAP will provide a more technical, detailed, and comprehensive description of the statistical analyses that will be computed, expanding on the protocol specified analyses.

Any deviation(s) from the original statistical plan should be described and justified in an amendment to the protocol and/or SAP as appropriate and referenced also in the final clinical trial report.

Further post-hoc evaluations of any exploratory endpoints may be conducted and reported separately.

#### 9.4.2. General considerations

#### 9.4.2.1. Descriptive Statistics

Continuous variables will be summarised using the following statistics: number of available data, number of missing values, mean (and/or geometric mean where applicable), standard deviation, median, Q1, Q3, minimum and maximum values. When relevant, confidence intervals (CIs) will be computed for the mean or the median.

Categorical variables will be summarised using number of available data, number of missing values, frequency counts for each category and corresponding percentage. Percentages will be calculated using the number of available data as the denominator (i.e., not including missing values). When relevant, CIs will be computed. If not otherwise specified in the SAP, the Wilson Score method will be used to compute CIs for proportions.

## 9.4.2.2. Inferential Statistics and Significance Testing

Between group comparisons will be performed using appropriate two-sided hypothesis tests at the 5% two-sided significance level, except if otherwise specified.

For continuous variables (either raw data or log-transformed data) the difference in means, the standard error and the 95% two-sided CI will be presented. In case of log-transformed variables, in addition to the previous statistics on the log-transformed data, the geometric means and geometric mean ratio and its 95% two-sided CI for the original variable will be presented. The Wilcoxon Rank-Sum test or the t-test or analysis of covariance will be used, depending on whether the endpoints are normally distributed. Details on the method used for each endpoint will be provided in the SAP. Methods for checking statistical model assumptions and alternative methods of analysis if the assumptions are not fulfilled will be described in the SAP.

For categorical variables, differences in absolute frequency and/or relative risks will be presented, with their 95% two-sided CIs. Except otherwise specified in the SAP, the Chi-square test (or Fisher exact test) will be used to compare frequencies between groups.

#### 9.4.3. Statistical Analysis

#### 9.4.3.1. Participant Accountability

The number of participants receiving SAB-176 or placebo, receiving Challenge virus, withdrawing from study (also split by reason for withdrawal), and completing the study, and the numbers in each analysis set will be summarized.

#### 9.4.3.2. Protocol Deviations

Participants data will be reviewed for major protocol deviations prior to main analysis database lock at a planned blinded data review meeting, and decisions will be documented within the meeting minutes. At this meeting, participants will be reviewed for their inclusion/exclusion in the different analysis sets.

#### 9.4.3.3. Demographic and Baseline Characteristics

Descriptive statistics of demographics (age, sex, height, weight, BMI, and ethnicity) will be presented by treatment group and across all participants. Medical history information will be listed. Other baseline characteristics will be defined in the SAP.

#### 9.4.3.4. Compliance to Study Intervention

Compliance with study intervention will be computed for each participant as proportion of prescribed study intervention actually taken.

#### 9.4.4. Primary Efficacy Analysis

The main estimator of the primary endpoint, the median VL-AUC of Influenza A/California/2009 H1N1 virus as determined by qRT-PCR on nasal samples (virology), will be analysed on the PP Analysis Set.

The calculation of the VL-AUC will be performed on log10-transformed PCR data using the trapezoidal summation rule based on actual time intervals in hours. Results below the lower limit of quantification (LLOQ) will be given values as detailed in the SAP.

Descriptive statistics and the 95% CI will be presented by treatment group. The difference between the two groups will be analysed using the Wilcoxon rank sum test. The two-sided p-value will be presented.

The primary efficacy analysis will be complemented by the analyses of a supportive estimator (Median VL-AUC of Influenza A/California/2009 H1N1 virus as determined by quantitative viral culture) as well two sensitivity estimators:

- Geometric mean of VL-AUC of Influenza A/California/2009 H1N1 virus as determined by qRT-PCR.
- Geometric mean of VL-AUC of Influenza A/California/2009 H1N1 virus as determined by quantitative viral culture.

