## 1.1. Study Schematic: On-study Participant Progression

\*NOTE: Release from quarantine is foreseen at Day 8 (8 days post-inoculation) in case no virus is detected by qualitative virus antigen test or polymerase chain reaction (PCR) (negative virus antigen test or PCR below Ct cut-off) and the participant has no clinically significant symptoms. If the participant continues to have clinically significant symptoms and/or detectable virus on Day 8, additional extended quarantine stay may be required at the discretion of the Investigator.

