# hvivo

CONFIDENTIAL

а	Study specific consent may occur on the day of admission, providing all required eligibility information has been collected through hVIVO Generic Screening process.
b	Only the applicable Inclusion / Exclusion criteria will be reviewed at each time point.
с	Height will be taken at Screening only.
d	Urine pregnancy tests will be performed in female participants of childbearing potential.
е	Vital signs will be taken at the same time(s) each day (±1 hour). On Day 1 the vital signs will be performed pre-infusion, and at 15 minutes, 30 minutes, 60 minutes, 90 minutes, 2 hours, 4 hours, and 8 hours after the start of the drug infusion.
f	Distribution of paper tissues and bags will start on Day -1, with the first collection on Day 0. Thereafter collection of tissues will occur at the same time points (±1 hour) with tissues distributed 24 hours ahead.
g	Assessments will be performed at the same time points (±1 hour) during quarantine.
h	A serum FSH test will be performed in all post-menopausal female participants.
i	Blood serum pregnancy test (β-hCG) will be performed in all female participants.
j	Blood may be drawn under non-fasted conditions. Repeat bloods may be drawn under fasted conditions if a lipid profile (triglyceride) or glucose is required (at Principal Investigators [PIs] discretion).
k	Blood will be collected for: i) virus serology (influenza antibody assay) to determine eligibility (at screening) and seroconversion (at Day -2 / -1 & Day 28), and ii) exploratory immune markers.
I	Nasopharyngeal swab or nasal wash for respiratory virus screen to assess for the presence of other respiratory viruses; if found positive the participant will not be eligible for the current quarantine.
m	Nasopharyngeal swabs (or nasal wash, if appropriate) will be collected for viral load assessments and exploratory immunology. Post inoculation nasal virology samples will be collected and used for qRT-PCR and viral culture assay.
n	Adverse events and concomitant mediations are reviewed throughout the study including pre- and post-infusion with IMP/placebo and pre- and post-inoculation.
0	Can be performed on Day -2 or Day -1. If admission at Day -1, all procedures scheduled for Day -2 can be performed on Day -1, as appropriate.
р	Optional and may be collected or not as per PI discretion for exploratory research.
q	Pre-infusion (only applicable to the first assessment on Day 1).
r	Post-dose ECG.

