#### Table 6: Methods for Analysis of Secondary Endpoints

Endpoints	Planned analysis
Peak viral load of VL-AUC of Influenza A/California/2009 H1N1 virus as defined by the maximum viral load determined by quantifiable qRT-PCR measurements in nasal samples starting two days post viral challenge (Day 2) up to discharge from quarantine.	Wilcoxon-rank-sum test (alternative: t-test if underlying assumptions valid)
Duration of influenza quantifiable qRT-PCR measurements in nasal samples.	Wilcoxon-rank-sum test (alternative: t-test if underlying assumptions valid)
Area under the curve over time of total clinical symptoms score (TSS-AUC) as measured by graded symptom scoring system (categorical and visual analogue scales).	t-test if underlying assumptions valid (alternative: Wilcoxon-rank- sum test)
Peak symptoms diary card score: peak total clinical symptoms score (TSS) as measured by graded symptom scoring system (categorical and visual analogue scales).	t-test if underlying assumptions valid (alternative: Wilcoxon-rank- sum test)
Peak daily symptom score: Individual maximum daily sum of symptom score.	t-test if underlying assumptions valid

Endpoints	Planned analysis
	(alternative: Wilcoxon-rank- sum test)
Number (%) of participants with Grade 2 or higher symptoms.	Chi-square test
Incidence of symptomatic infection due to Influenza A/California/2009 H1N1 virus, compared to placebo as measured by: RT-PCR-confirmed symptomatic influenza infection defined as:	Chi-square test (on the composite and each component)

RT-PCR-confirmed influenza infection, AND

Clinical symptoms

	

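### The primary test of VL-AUC is valid but ignores baseline values already collected on everyone, and section 9.4.4 does not say when the AUC starts or ends

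*Combined protocol and SAP*

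**What the plan says.** **Primary test.** Section 9.4.4 takes the median qRT-PCR VL-AUC in the Per Protocol set as the main estimator. It says that "Descriptive statistics and the 95% CI will be presented by treatment group". The next sentence is the one that matters here: it names the Wilcoxon rank sum test for the difference between arms, with no covariate. The two geometric-mean sensitivity estimators name none either. Section 9.4.2.2 lists analysis of covariance among the general options, depending on normality, and leaves the method for each endpoint to the SAP.

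**Baseline data.** The Schedule of Activities (1.2) has virology twice on Day 1. Footnote q marks the first of these: "Pre-infusion (only applicable to the first assessment on Day 1". Challenge is on Day 0 and infusion on Day 1, so this swab follows inoculation and precedes treatment. Antibody to the challenge virus is measured at screening and at Day -2/-1 (footnote k). HAI is also run on the pre-infusion PK sample (8.16.3). Eligibility limits the titre: "he/she must have no or low pre-existing serum levels of antibodies specific to the Challenge virus" (8.16.2).

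**AUC window.** Section 9.4.4 prescribes a trapezoid on log10 data over actual hours but gives no first or last sample. A window appears only in Table 6, for peak viral load: "starting two days post viral challenge (Day 2) up to discharge from quarantine". Section 1.1 adds: "If the participant continues to have clinically significant symptoms and/or detectable virus on Day 8, additional extended quarantine stay may be required", at the investigator's discretion.

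**The concern.** Table 1 puts the chance of infection at about 65%, so of 60 inoculated participants about 39 (0.65 × 60) would be infected and 21 would not. The Per Protocol set does not require infection. Variation in whether the inoculation took, and in prior immunity, therefore enters the primary comparison as noise. A swab taken before treatment and a baseline titre are the two measured quantities most likely to explain some of it, and neither is used.

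The open window is a separate matter. If the AUC includes samples from before the infusion, part of the outcome is time that treatment cannot change, which dilutes the effect. If an endpoint runs to actual discharge, and discharge waits on viral clearance, heavy shedders can be observed for longer than others.

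**Working it through.** **1. Reproduce the stated design.** Section 9.2 says that 30 per arm "will allow detecting a 60% relative reduction in the qRT-PCR-AUC virology with SAB-176 assuming an 81% coefficient of variation in the control arm", at 80% power and two-sided 5%. In units of the control mean, the difference is 0.60 and the SD is 0.81, taken as equal in both arms.

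- Standardised effect: d = 0.60 / 0.81 = 0.741.
- Normal approximation: power = Φ(d × √(30/2) − 1.96) = Φ(2.869 − 1.96) = 81.8%; 29 per arm are needed for 80%.
- t-test: 80.5% at 30 per arm; 29.6 per arm, rounded up to 30, are needed for 80%.
- Planned Wilcoxon test, simulated on normal data (20,000 runs): 78.6%.

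The stated figure reproduces with no covariate adjustment.

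**2. Effect of adjustment.** Let r be the (multiple) correlation of the covariates with VL-AUC within arms. The documents do not give it, so the values below are assumptions. The residual SD becomes 0.81 × √(1 − r²), so d becomes 0.741 / √(1 − r²). The unadjusted trial of equal precision has 60 / (1 − r²) participants.

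| r (assumed) | Variance removed | Equivalent N | t-test power, 30 per arm |
|---|---|---|---|
| 0 | 0% | 60 | 80.5% |
| 0.1 | 1% | 61 | 80.9% |
| 0.2 | 4% | 62.5 | 82.1% |
| 0.3 | 9% | 66 | 84.1% |
| 0.4 | 16% | 71 | 86.8% |
| 0.5 | 25% | 80 | 90.3% |

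These are normal-theory figures. They indicate the scale of the gain for a rank-based version and are not its exact power.

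**3. Effect of counting time before treatment.** Suppose a share w of the control AUC accrues before infusion (assumed; not in the documents), treatment cannot alter it, and the SD stays at 0.81. The detectable reduction becomes 0.60 × (1 − w). Normal approximation, 30 per arm:

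- w = 0: 0.60, power 81.8%.
- w = 5%: 0.57, power 77.8%.
- w = 10%: 0.54, power 73.3%.

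**4. End of the window, passages side by side.**

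- Schedule of Activities: virology twice daily on Days 1 to 7 and once on Day 8, then only at an early withdrawal visit.
- Table 6: peak viral load runs to discharge.
- Section 1.1: discharge may be delayed for detectable virus.
- Section 8.12: tissue collection continues through an extended stay. Sections 8.17 and 8.17.3 contain no matching rule for virology.

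So Table 6 allows the observation period for peak to depend on the outcome, but only if unscheduled swabs are taken and used. For scale, one extra day at constant viral load adds 1/7, about 14%, to a 7-day AUC. That is an upper-end illustration, since Table 1 expects virus usually to be gone from the nose by discharge.

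**The case against.** Adjustment is a choice and not a correction. A prespecified Wilcoxon test in a randomised trial is valid, and its error rate already allows for chance imbalance. A reader might infer that the trial gives power away or is underpowered for lack of covariates. The documents do not support that: the planned power reproduces, and the gain rests entirely on an unknown r. At 0.2 or less it is under 2 points.

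There are also reasons to expect modest correlations. Only participants with no or low titres are eligible, which narrows the range of titre. The Day 1 swab comes about one day after inoculation, and many values may lie below the LLOQ. Ordinary ANCOVA would replace the stated median estimator with an adjusted mean, and 9.4.2.2 ties the choice of method to normality, which is doubtful with about a third uninfected. All of this stands. It is why the request is for a rank-based adjustment and why no particular gain is promised.

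The planned ITT-I set partly addresses uninfected participants. It does not replace baseline adjustment, because infection is judged largely on samples taken after treatment.

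A reader might also infer that follow-up for the primary endpoint depends on the outcome. That is not shown. The discharge wording in Table 6 covers secondary peak viral load only, the Per Protocol set is defined by completion to Day 8, and no virology is scheduled after Day 8 apart from early withdrawal.

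Finally, several sections defer detail to the SAP, and the document reviewed contains no separate SAP text. The gaps are therefore shown for the protocol only.

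**Conclusion.** The primary analysis is valid as written. Two improvements are nevertheless available without new data.

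First, adjustment for the pre-infusion viral load and baseline titre may improve precision: from 80.5% power to about 82% at r = 0.2, 84% at 0.3 and 90% at 0.5, all under assumed correlations and normal theory. Titre may contribute little.

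Second, the VL-AUC window is undefined in 9.4.4, and this is the firmer point. Counting time before treatment would cost about 4 points of power if it made up 5% of the control AUC, and about 8.5 points at 10% (assumed shares, SD unchanged). Outcome-dependent observation time is a risk for peak viral load and has not been shown for the primary endpoint.

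**What to change.** Before unblinding, state in the SAP:

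- **Primary test:** rank ANCOVA of VL-AUC on Day 1 pre-infusion log10 viral load and baseline antibody titre. For example, rank the outcome and covariates over both arms, regress the outcome ranks on the covariate ranks, and compare the residuals between arms. Name the titre sample and assay to be used, and apply the SAP's LLOQ rule to the viral load covariate. Keep the medians as the descriptive summary.
- **Sensitivity:** the unadjusted Wilcoxon test.
- **Window:** compute VL-AUC, peak and duration from a fixed post-infusion start (the first sample after infusion, expected to be the second Day 1 swab) to the scheduled Day 8 sample. Use the pre-infusion swab as a covariate and not as outcome. Exclude any virology from an extended stay from these endpoints, and align Table 6 with this window.

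The cost is SAP wording and the matching edit to Table 6. No sample, visit or participant is added.
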